Once subjects are engaged in care at the treatment clinic, they will continue to receive SUBLOCADE for 6 months. The second 300 mg injection will be administered on Day 8 (-0/+4 days) after the first injection, with subsequent 300 mg injections administered at 28-day (-2/+4 days) intervals over approximately 6 months for a total of 7 injections. If necessary, for tolerability, the dose of SUBLOCADE can be reduced to 100 mg. All subjects will receive site standard psychosocial therapy at least weekly during the first 3 months of treatment, and twice monthly thereafter if clinically stable.

All subjects will complete an End of Treatment (EOT) / Early Termination (ET) visit 28 days after their last injection of SUBLOCADE. Within 3 months prior to or at the EOT visit, the Investigator or a medically qualified sub-investigator will discuss the subject's available treatment options and arrange referral. All subjects will receive a safety follow-up telephone call, 30 days after their EOT/ET visit to assess AEs, SAEs, pregnancy status (if applicable) and concomitant medications. Subjects who decline to continue in medication assisted treatment (MAT) will receive monthly safety follow-up phone calls for an additional 5 months (6 months total) to assess SAEs, pregnancy status (if applicable) and concomitant medications.

Primary Endpoint(s):

The primary endpoint of this study is:

- Time to repeat OD or opioid-related death. Repeat OD or opioid-related death will be measured from electronic medical records and state death registries.
- Additional comparisons on repeat OD and death rates will be made to concurrent patients who decline to participate in the SUBLOCADE injection.

Secondary Endpoint(s):

The key secondary endpoint of the study is:

- Treatment engagement as measured by attending the outpatient clinic and receiving subsequent buprenorphine treatment at 3 and 6 months.

The secondary endpoints of this study are:

- Numbers and percent of subjects in treatment at 3 and 6 months after opioid OD.

Exploratory Endpoints:

The exploratory endpoints of this study are:

- Opioid craving in subjects as measured by Craving Visual Analog Scale (VAS) scores.
- Illicit opioid use as measured by urine drug screen (UDS) results.
- Genetic predictors of treatment response and OD.

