3.2 Secondary

The key secondary endpoints of the study are:

- Numbers and percent of patients in buprenorphine treatment at 3 and 6 months after opioid OD comparing patients who have primarily intravenous to non-intravenous opioid use.

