8.1 Demographics and Medical History

A detailed medical history will be obtained during the screening period. This will include information regarding the subject's complete history of relevant medical conditions, diagnoses, procedures, treatments, detailed history of drug use and any other noteworthy medical information. Any updates to medical history information made available during the course of the study will be captured.

8.1.1 DSM-5 Checklist for OUD, AUD and SUD and Mini-International Neuropsychiatric Interview (DSM 5 version)

At screening, the DSM-5 Checklist will be performed to assess for the presence and severity of OUD, AUD and SUD and will be reviewed by the PI or Sub-Investigator. At visit 2, the standardized diagnostic tool of the Mini-International Neuropsychiatric Interview (M.I.N.I), DSM-5 version (7.0.2) ([Sheehan, 2016](#)) will be used to screen for other DSM-5 substance-use disorders or other psychiatric co-morbidities.

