14.4 Analysis Populations

14.4.1 Treatment Population

The Treatment Population includes all subjects who receive at least 1 dose of study medication. This population will be used for all safety and efficacy analyses. In the safety analyses, subjects will be analysed according to treatment actually received.

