14.7.2 Secondary/Exploratory Endpoint Analysis

Treatment retention at 3 and 6 months will be analysed utilizing a logistic regression, comparing subjects who have primarily intravenous to non-intravenous opioid use as determined using the MINI.

The analysis of the exploratory endpoints (incidence rate of repeat OD, illicit opioid use as measured by UDS and opioid craving, as measured by the OC-VAS) is detailed in Table 2.

These analyses will be performed using the treatment population.

A summary of the primary, secondary, and exploratory endpoint analyses is shown in Table 2.

Table 2 Summary of Efficacy Analysis Strategy

Endpoint	Statistical Method	Analysis Population	Missing Data Approach	Analysis Timepoint
Primary Efficacy Endpoint:				
Repeat OD or Death	Propensity scores within Cox PH Regression	Treatment	No imputation	EOT (6 months)
Secondary Efficacy Endpoints:				
Treatment retention at 3 and 6 months	Logistic Regression	Treatment	No imputation	EOT (6 months)
Exploratory Endpoints:				
Illicit opioid use as measured by urine drug screen (UDS) results	Hierarchical generalized linear modeling (HGLM)	Treatment	Missing UDS during treatment will be imputed as non-negative for opioids. Missing UDS if lost to follow-up will be imputed as missing.	EOT (6 months)
Opioid craving in subjects as measured by Craving Visual Analog Scale (VAS) scores.	Logistic Regression, ANCOVA	Treatment	No imputation	EOT (6 months)
Genetic predictors of treatment response and repeat OD.	Logistic Regression, ANCOVA	Treatment ^a	No imputation	EOT (6 months)
Predictability of treatment response based on impulse control as measured by decision making in the delay discounting task.	Logistic Regression, ANCOVA	Treatment	No imputation	EOT (6 months)
Retention in treatment between ED initiated Suboxone/Sublocade compared to Outpatient initiated Suboxone/Sublocade	Cox PH Regression	Treatment	No imputation	EOT (6 months)

^a This analysis will only include subjects within the treatment population that consented to participate in the PGx sub-study.

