22 APPENDICES

22.1 Appendix 1 –Schedule of Events – Visit 1 (In ED, inpatient unit or Outpatient Clinic within 7 days (168 h) after OD

Procedure / Assessment	Screening Procedures (Visit 1)	Treatment Period (Visit 1)			Sublocade Dosing	Post-Sublocade dose Procedures
		Pre-Suboxone dose Procedures	Suboxone Dosing	Post-Suboxone dose Procedures		
Informed Consent	X					
Inclusion/Exclusion Criteria	X					
Demographics	X					
Medical History	X					
Brief Physical Examination	X					
Concomitant Medications Assessment	X					
Vital Signs	X					
Height/Weight/BMI	X					
Breathalyzer	X					
Urine Pregnancy Test	X ^b					
DSM-5 OUD/AUD/SUD Checklist	X					
Liver function laboratory tests (STAT)		X ^d				
COWS		X ^e		X		X
OC-VAS		X ^e		X		
Delay Discounting Task		X		X		
Opioid Demand Task		X		X		
SUBOXONE Test Dose			X ^{f,g}			
SUBLOCADE Dose					X	
PGx Sampling				X ^a		
AE Assessment		X		X ^g		X
Clinic appointment visit scheduled for next dose						X

AE = adverse event; COWS = Clinical Opiate Withdrawal Scale; MINI = Mini-International Neuropsychiatric Interview

- a. PGx samples will only be taken from subjects that consent to participate in the optional PGx sub-study.
- b. Urine pregnancy test, only for females of child-bearing potential. Results must be available and reviewed prior to Suboxone treatment.
- c. Subjects will be included in the study only after it is determined that subject meets all inclusion criteria and none of the exclusion criteria.
- d. STAT Local labs will be used for screening liver function tests. Samples must be drawn prior to dosing and will include ALT, AST and bilirubin. Abnormal liver function tests (LFTs) will be followed at clinic visits according to investigator's judgement. Liver function tests obtained for clinical reasons will also be used for research purposes if we are unable to obtain blood for research purposes. An etiological evaluation will be performed if a hepatic adverse event is suspected.
- e. The COWS and OC-VAS will be completed after consent but prior to first administration of SUBOXONE sublingual film.
- f. Day 1 SUBOXONE/SUBLOCADE Regimen includes supervised administration of 4mg/1 mg SUBOXONE sublingual film, followed by 300 mg SUBLOCADE administration.
- g. Subjects will be assessed for adverse events predose and 1-2 hours postdose depending on RASS score prior to discharge.

22.2 Appendix 2 – Treatment Clinic Schedule of Events – (Week 1 Day 2 – Week 25 Day 169)

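### The IV/non-IV group for the retention comparison comes from an interview held only after the first dose, so subjects who never return are known failures with no stated group

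*Combined protocol and SAP*

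**What the plan says.** Section 3.2 states the key secondary endpoint as the number and percent of "patients in buprenorphine treatment at 3 and 6 months after opioid OD comparing patients who have primarily intravenous to non-intravenous opioid use". Section 14.7.2 analyses it by logistic regression, "comparing subjects who have primarily intravenous to non-intravenous opioid use as determined using the MINI". No other source for the grouping is given there.

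Section 8.1.1 fixes the timing: "At visit 2, the standardized diagnostic tool of the Mini-International Neuropsychiatric Interview" is used. Its stated purpose is that it "will be used to screen for other DSM-5 substance-use disorders or other psychiatric co-morbidities"; route of use is not mentioned. Appendix 2 marks the MINI once, at Visit 2 (Day 2, window -0/+3, so Days 2 to 5). Appendix 1, which covers Visit 1 and the first SUBLOCADE dose, has a row for the "DSM-5 OUD/AUD/SUD Checklist" but none for the MINI.

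Section 14.4.1 sets the population: "The Treatment Population includes all subjects who receive at least 1 dose of study medication". On missing data, Table 2 specifies no imputation for retention, while Section 14.8 says that missing covariates will be multiply imputed. Section 14.8 also treats subjects who cease to appear as having stopped at their last visit.

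Two places suggest that route is known before dosing. Section 8.1 requires a "detailed history of drug use" at screening, and Section 14.7.4 classifies injectors and non-injectors at Visit 1 for a repeat of the primary analyses. The synopsis also lists route of administration as a covariate in the primary Cox model.

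**The concern.** A baseline grouping should be fixed before treatment and be available for everyone in the denominator. Here it depends on attending a visit after the first dose. For subjects treated in the ED or inpatient unit, Visit 2 is the first clinic visit, and attending that clinic is part of what the synopsis means by engagement. A subject who is dosed and never comes back has a known outcome (not retained) but no group.

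What is at stake is how the IV versus non-IV retention result is read. If these subjects leave the model, early failures leave with them. Each group's retention is then too high, and the comparison can move towards or away from the null.

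**Working it through.** The plan gives no figure to reproduce, and the documents state no no-show, route or retention shares. Every input below is an assumption, with 50 subjects per group (about 100 are to be enrolled).

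**Notation, per group (1 = IV, 0 = non-IV).** m = share never returning after Visit 1. r = retention among returners. p = (1 − m) × r = retention among all dosed. s = m/(1 − p) = share of non-retained subjects who have no MINI group.

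- True OR = odds(p1)/odds(p0)
- OR with never-returners excluded = odds(r1)/odds(r0)
- Excluded OR / true OR = (1 − s0)/(1 − s1)

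The last factor holds only if no retained subject lacks a MINI. It equals 1 when s1 = s0.

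**Lead case: m = 40% IV, 20% non-IV; r = 50% in both.**

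- All dosed: 15 retained and 35 not (IV, 30%); 20 and 30 (non-IV, 40%). OR = (15/35)/(20/30) = 0.64. Woolf SE = √(1/15 + 1/35 + 1/20 + 1/30) = 0.423, so the 95% CI is 0.28 to 1.47.
- Never-returners excluded: 15 and 15; 20 and 20. OR = 1.00. SE = √(2/15 + 2/20) = 0.483, CI 0.39 to 2.58. Retention reads 50% in both groups.
- Check: s1 = 20/35 = 57%, s0 = 10/30 = 33%. Factor = 0.667/0.429 = 1.56, and 0.643 × 1.556 = 1.00.

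**Other assumed cases (never returning, IV/non-IV).**

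| Never return | Retention assumption | True OR | OR with exclusion |
|---|---|---|---|
| 20%/10% | 50% of returners in both | 0.81 | 1.00 |
| 20%/40% | 50% of returners in both | 1.56 | 1.00 |
| 10%/20% | 50% of returners in both | 1.23 | 1.00 |
| 30%/30% | 60% vs 40% of returners | 1.86 | 2.25 |
| 40%/20% | 40% of all dosed in both | 1.00 | 2.00 |
| 20%/10% | 40% of all dosed in both | 1.00 | 1.25 |
| 40%/20% | 30% of all dosed in both | 1.00 | 1.67 |
| 20%/10% | 30% of all dosed in both | 1.00 | 1.20 |

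Reversing the no-show shares in the last four rows gives 0.50, 0.80, 0.60 and 0.83. With equal no-show and equal retention there is no bias.

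**Imputing route in the lead case.** The 30 never-returners are allocated by expected value, using the 35 non-retained returners (15 IV, 20 non-IV).

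- From outcome alone: P(IV | not retained) = 15/35, so 12.86 are allocated to IV and 17.14 to non-IV. OR = (15/27.86)/(20/37.14) = 1.00, the same as exclusion.
- With a Visit 1 injector item that agrees 90% with route: P(IV | item positive) = 13.5/15.5 and P(IV | item negative) = 1.5/19.5. Among never-returners 19 are positive and 11 negative, so 17.4 go to IV and 12.6 to non-IV. OR = (15/32.4)/(20/32.6) = 0.75.
- With 95% agreement: 18.6 and 11.4. OR = (15/33.6)/(20/31.4) = 0.70.
- Route recorded at Visit 1: 0.64.

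**The case against.** The strongest reply is that the plan need not lose anyone. In a logistic model of retention, route is a covariate, and Section 14.8 says missing covariates are multiply imputed. The no-imputation entry in Table 2 sits in a row defined by the endpoint and fits an outcome reading. This largely stands: a reader might infer that the plan excludes never-returners, but the documents do not say so, and imputation is the more natural reading. It does not close the point. Section 14.8 names no predictors, and imputing from the outcome alone gives the same biased result as exclusion.

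A reader might also infer that everyone who misses Visit 2 lacks a group. Section 6.4.4 requires staff to try to reschedule missed visits, so those who come back may still have the MINI. The firm gap is the never-returners. If some retained subjects did lack a MINI, the factor would become [(1 − t1)/(1 − t0)] × [(1 − s0)/(1 − s1)], with t the share of retained subjects without one. Assumed t of 20% versus 5% with equal s gives 0.80/0.95 = 0.84, so equal s alone would not guarantee an unbiased odds ratio.

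A third tempting inference is that route cannot be known before dosing. Sections 8.1 and 14.7.4 point the other way, so the defect is the choice of source, not missing data. Injector status is not quite the same as primarily intravenous use, so it supports the grouping but does not replace it.

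Finally, this is an unpowered comparison within one arm, and the intervals in the lead case overlap heavily. That stands and limits the weight of the point.

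**Conclusion.** The point holds as a cheap improvement. Section 14.7.2 makes group membership depend on early attendance, which is part of the outcome, and leaves subjects who never return after Visit 1 without a group. Exclusion overstates group-specific retention. It biases the odds ratio, in either direction, when the share of non-retained subjects lacking a group differs between IV and non-IV. Imputation under Section 14.8 helps only as far as Visit 1 route information enters the model.

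The lead example (0.64 against 1.00, or 0.70 to 0.75 with a good Visit 1 item) shows what is possible and does not forecast the trial. It rests wholly on assumed shares, and most of the shifts are within sampling error at this size.

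A reader might infer that the key secondary result as a whole, or the primary result, is compromised. The documents do not support that. The MINI grouping is specified only for the retention comparison. The synopsis states its key secondary engagement endpoint without grouping and separately lists "Numbers and percent of subjects in treatment at 3 and 6 months after opioid OD"; never-returners count in both. The primary comparison is SUBLOCADE against controls and does not use this grouping.

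**What to change.** In Section 14.7.2:

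- Define primary route (IV versus non-IV) from the pre-dose Visit 1 drug-use history for every dosed subject. Add one primary-route item to the Visit 1 form if it is not already recorded.
- Use the MINI-based grouping only as a sensitivity analysis.
- Keep all dosed subjects in the denominator and count those who never return as not retained.
- Where route is still missing, impute it under Section 14.8 with Visit 1 injector status, drug history and the retention outcome in the model. State that the no-imputation entry in Table 2 refers to the outcome.

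The cost is SAP wording and at most one form item. For subjects already enrolled, route has to come from Visit 1 source notes where it was recorded.

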14.7.2.1 Health Economics & Outcomes Analyses

Treatment Effectiveness Assessment (TEA)

HEOR endpoints relating to the TEA will be described as change from baseline score to each follow-up assessment and end of treatment (EOT). Absolute scores by study visit will also be reported and compared between treatment groups. The absolute score and/or change from baseline score at EOT will be considered the primary variable of interest in these analyses.

Baseline will be defined as the last assessment on or before Week 3 Day 15±4 (Visit 4). (See Appendix 2- Treatment Clinic Schedule of Events)

MEDICATION SATISFACTION QUESTIONNAIRE (MSQ)

The percentage of subjects reporting each response on the MSQ will be reported by study visit and EOT. The percentage of subjects reporting that they are satisfied (score 5-7) at the EOT will be considered the primary variable of interest in these analyses.

WORK PRODUCTIVITY ASSESSMENT INSTRUMENT: SPECIFIC HEALTH PROBLEM (WPAI:SHP)

For the WPAI:SHP, the percentage of patients employed, percentage absenteeism, percentage work impairment, and percentage activity impairment will be reported at baseline, each follow-up assessment and EOT by treatment arm. The change in percent employed from baseline to each follow-up assessment will be assessed. Among those employed at baseline and the respective follow-up assessments, the changes from baseline in percentage absenteeism, percentage work impairment and percentage activity impairment at each follow-up assessment will be assessed. The change in percent employed from baseline to EOT; and among those employed at baseline and EOT, the changes in percentage absenteeism, percentage work impairment and percentage activity impairment from baseline to EOT will be considered as primary variables of interest in these analyses.

Baseline will be defined as the last assessment on or before Week 3 Day 15±4 (Visit 4). (See Appendix 2- Treatment Clinic Schedule of Events)

HEALTHCARE RESOURCE UTILIZATION QUESTIONNAIRE(HCRUQ)

Frequency of use by HCRUQ type will be summed throughout the study period, from Week 1 to EOT (or last visit with available data for subjects who discontinue treatment prematurely), to arrive at a total use while in the study. The incidence of HCRUQ by type will be assessed, dividing by the total amount of follow-up time in each group. Types of hospitalisations, emergency room, and outpatient service visits will be categorized (e.g., medical, surgical, psychiatric). Hospital days will be calculated as the sum of all inpatient days during the study.

For continuous measures, 95% confidence intervals will be provided for comparisons of statistics between treatments. Unless otherwise specified, the absolute value of continuous outcome measures will be analysed using a mixed model for repeated measures (MMRM). A test of proportions (for example: exact test) will be used to evaluate treatment differences for categorical outcome variables.

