8.9.1 Treatment Effectiveness Assessment (TEA)

The Treatment Effectiveness Assessment (TEA) ([Ling 2013](#)) elicits subject responses that help the subject and the clinician to quickly gauge subject progress in treatment and in recovery. This progress is determined according to the subject's sense of what is important within four domains established by prior research. Improvement in each of the four recovery-oriented domains (substance use, health, lifestyle, and community) can be assigned a value of 1 (not improved or little improved) to 10 (very much improved) by the subject. The total score of improvement since treatment start is the sum of the responses to the four TEA domains, ranging from 4 (no measurable improvement or worse) to 40 (significantly improved). Subjects provide both numerical responses and representative details on their substance use, health, lifestyle, and community. In other words, the TEA assesses treatment progress and recovery, based on the subject's perspective.

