14.9 Analysis of Safety

Safety variables will include AEs, concomitant medications, laboratory tests (haematology, chemistry and urinalysis), vital signs, and medical history. Safety variables will be analysed on the treatment population using descriptive statistics for continuous endpoints (e.g. mean, median, SD, minimum and maximum) and frequency counts with percentages for discrete endpoints.

Baseline is defined as the last available assessment prior to dosing on Week 1 Day 1 (Visit 1).

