Appendix 2 - Treatment Clinic Schedule of Events – (Week 1 Day 2 – Week 25 Day 169)

Procedure / Assessment	Treatment Period									30-Day Safety Follow-up Telephone Call ^d
	Visit 12	Visit 13	Visit 14	Visit 15	Visit 16	Visit 17	Visit 18	Visit 19	End of Treatment / Early Term	
	Wk 11 D 71 (±4) D	Wk 12 D 78 (±4) D	Wk 13 D 85 (±4) D	Wk 14 D92 (-2/+4) D	Wk 16 D106 (±4) D	Wk 18 D120 (-2/+4 D	Wk 20 D134 (±4) D	Wk 22 D148 (-2/+4) D	Wk 25 D 169 (±4) D	Wk 29 Day 199 (±4) D
Counselling	X	X	X	X	X	X	X	X	X	
Urine Drug Screen	X	X	X	X	X	X	X	X	X	
Delay Discounting Task		X							X	
Opioid Demand Task		X							X	
OC-VAS ^a	X	X	X	X	X	X	X	X	X	
COWS	X	X	X	X	X	X	X	X	X	
TEA	X					X			X	
HCRUQ	X			X		X		X	X	
MSQ	X					X			X	
Employment Question	X					X			X	X footnote
AE Assessment	X	X	X	X	X	X	X	X	X	X
Concomitant Medications Assessment	X	X	X	X	X	X	X	X	X	
Vital Signs	X	X	X	X	X	X	X	X	X	
Urine Pregnancy Test ^b	X	X	X	X	X	X	X	X	X	X
SUBLOCADE Injection				X		X		X		
Liver function laboratory testing			X				X		X	

- OC-VAS will be assessed prior to SUBLOCADE injection
- Urine pregnancy test, only for females of child-bearing potential. Results will be obtained prior to SUBLOCADE injection.
- All subjects will receive a safety follow-up telephone call 30 days after their EOT/ET visit to assess AEs, SAEs, pregnancy status (if applicable) and concomitant medications. Subjects who decline to continue in MAT will receive monthly safety follow-up phone calls for an additional 5 months (6 months total) to assess SAEs, pregnancy status (if applicable) and concomitant medications.

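### The TEA baseline falls at Visit 4 (Day 15±4), on treatment, so TEA change from baseline leaves out any change between Visit 2 and Visit 4

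*Combined protocol and SAP*

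**What the plan says.** **Baseline rule.** Section 14.7.2.1, under the TEA, states: "Baseline will be defined as the last assessment on or before Week 3 Day 15", and the sentence goes on to give a window of ±4 days and to name Visit 4. The same sentence is repeated for the WPAI:SHP.

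**TEA variable.** The same section plans change from baseline to each follow-up and to EOT, as well as absolute scores by visit. It adds: "The absolute score and/or change from baseline score at EOT will be considered the primary variable of interest in these analyses". Its closing paragraph says that continuous outcomes are by default analysed on their absolute values with an MMRM.

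**What TEA measures.** Section 8.9.1: "The total score of improvement since treatment start is the sum of the responses to the four TEA domains". The total runs from 4 to 40.

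**Dosing.** Appendix 1 gives the Day 1 regimen as a supervised SUBOXONE film "followed by 300 mg SUBLOCADE administration". The Synopsis adds: "The second 300 mg injection will be administered on Day 8 (-0/+4 days) after the first injection".

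**Schedule.** Appendix 2 marks TEA at Visits 2, 4, 12 and 17 and at EOT. It marks WPAI:SHP at Visit 2 only. Appendix 1 lists neither instrument before the first dose.

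**The concern.** A baseline should describe the subject before, or as close as possible to, the start of the treatment being assessed. The TEA rule takes the latest value in the first 15±4 days, not the earliest. For a subject who attends Visit 4, the reference value is then itself an on-treatment outcome, on a scale that already scores improvement from the beginning of treatment.

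Two things are at stake for the TEA change score:

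- Any movement between Visit 2 and Visit 4 disappears from it. Section 1.1.2 explains that the second injection was placed on Day 8 to increase potential benefit, so this early interval is of interest.
- The day of baseline depends on whether the subject attended Visit 4, which is on-treatment behaviour. Subjects who attended and subjects who did not are measured over different intervals and then pooled.

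Section 14.9 uses the last value before Day 1 dosing as the baseline for safety variables. No reason is given for choosing a later reference for TEA.

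**Working it through.** The plan states no figure to reproduce. The check applies the baseline rule to the visit schedule.

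| Event | Source | Nominal day | Window |
|---|---|---|---|
| Injection 1 (Visit 1) | Appendix 1 | 1 | – |
| Visit 2: TEA, WPAI:SHP | Appendix 2 | 2 | 2 to 5 |
| Injection 2 (Visit 3) | Synopsis, Appendix 2 | 8 | 8 to 12 |
| Visit 4: TEA | Appendix 2 | 15 | 11 to 19 |
| EOT: TEA | Appendix 2 | 169 | 165 to 173 |

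**Step 1: which TEA value the rule selects.** Up to Visit 4 there are two scheduled TEA values, at Visits 2 and 4. The later one is Visit 4 if attended, and Visit 2 otherwise.

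**Step 2: how much treatment precedes it.**
- Visit 4 is 15 − 1 = 14 days after injection 1 (range 11 − 1 = 10 to 19 − 1 = 18).
- Visit 4 is nominally 15 − 8 = 7 days after injection 2. The windows of Visits 3 and 4 overlap on Days 11 and 12, so this order assumes that visits occur in sequence and that injection 2 was given.
- Visit 2 is 2 − 1 = 1 day after injection 1 (up to 5 − 1 = 4) and before injection 2.

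**Step 3: what the change score loses.** For a Visit 4 attender with a Visit 2 value:

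EOT − V4 = (EOT − V2) − (V4 − V2)

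The term V4 − V2 is removed in full. The same holds with Visit 12 or Visit 17 in place of EOT. In nominal time the change to EOT covers 169 − 15 = 154 days, not 169 − 2 = 167.

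**Step 4: size.** The documents give no TEA means, SDs or time course, so this is an assumed illustration only. Take V2 = 4 and EOT = 28, a gain of 24, and let f be the share of that gain reached by Visit 4. Reported change = (1 − f) × 24.

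| f | V4 | Reported change |
|---|---|---|
| 0 | 4 | 24 |
| 0.25 | 10 | 18 |
| 0.5 | 16 | 12 |
| 0.75 | 22 | 6 |
| 1 | 28 | 0 |

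If scores fell between Visits 2 and 4, the reported change would exceed 24. The absolute EOT score is 28 in every row.

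**Step 5: mixed baselines.** Take two subjects with the same assumed course of 4, 16 and 28 at Visit 2, Visit 4 and EOT. The one who attends Visit 4 has a change of 28 − 16 = 12. The one who misses it has 28 − 4 = 24. They differ only in attendance.

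**Step 6: the same rule applied to WPAI:SHP.** Visit 2 is its only scheduled assessment up to Day 19, so the rule selects Visit 2. A later baseline would need an unscheduled assessment.

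**The case against.** **The absolute score keeps the early gain.** The plan allows the absolute EOT score as the main TEA variable, reports scores by visit, and models absolute values by default. Because the scale already counts from the start of treatment, that score retains anything gained in the first two weeks. This stands, and it confines the point to the change score. It does not remove the point: change to every follow-up is still planned, and the and/or wording does not settle which variable leads.

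**Visit 2 is not pre-treatment either.** This stands. Visit 2 follows the first injection, and no TEA is scheduled before dosing. Visit 2 is only the earliest value available. The comparison with section 14.9 is therefore limited, since safety variables do have pre-dose values.

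**Falling back on Visit 4 also mixes baseline days.** This is true for subjects without a Visit 2 value. The difference is that the earliest value becomes the default and the exceptions are identified. The documents give no attendance rates, so the extent of mixing under either rule is unknown.

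**The Visit 4 limit may be meant to rescue subjects who miss Visit 2.** The plan does not say so. If that is the intent, taking the first value in the window achieves it without setting Visit 2 aside.

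**A stronger reading of the WPAI:SHP.** A reader might infer from the repeated sentence that its baseline, too, follows two injections. That would matter, because its main variables are changes "from baseline to EOT will be considered as primary variables of interest in these analyses". Appendix 2 does not support this, as Step 6 shows. The later part of the schedule has a row labelled "Employment Question" and no WPAI:SHP row, but that concerns follow-up data and is a separate matter from baseline.

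**Conclusion.** The point holds for TEA change from baseline only. For Visit 4 attenders the baseline is an on-treatment value, nominally 14 days after the first injection and 7 days after the second, and any change from Visit 2 to Visit 4 is lost from all later change scores. For those who miss Visit 4, baseline reverts to Day 2. This rests on the schedule as written, on visits occurring in order and on the second injection having been given.

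A reader might also infer that the TEA effect is cut by a known amount, such as half. The documents do not support any figure: the loss ranges from nothing to the whole change, depending on how much happens by Visit 4.

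Severity is low. TEA is an exploratory endpoint (section 3.3) and does not appear in Table 2. The primary endpoint, the treatment-retention analysis and the absolute TEA scores are unaffected.

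**What to change.** In section 14.7.2.1:

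- Define the TEA baseline as the first assessment after enrolment, scheduled at Visit 2.
- Use the Visit 4 value only when Visit 2 is missing, and flag those subjects in the listings and summaries.
- State that Visit 2 is the earliest scheduled TEA value and that it follows the first injection, so the change score is not read as change from an untreated state.
- For the WPAI:SHP, name Visit 2 as baseline so that the text agrees with Appendix 2. This does not change which value is used on the current schedule.

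The cost is a few sentences, made before analysis. The Visit 2 data are already scheduled, so no new assessment, visit or sample size change is needed.
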